10. PRODUCTS, DEVICES, TECHNIQUES AND TOOLS

Devices

PCR based tests

PCR involves the repeated logarithmic amplification of specific areas of the bacterial chromosome using an iterative process of hybridisation of replication primers, amplification from these primers of the target DNA and separation of the nascent DNA. Real-time detection of the amplified DNA is by incorporation of a fluorescent marker which is quantitatively measured within the PCR thermocycler.

Version 1.0 22nd December 2015 GBS2 Page 56 of 81

In GBS1, we found the highest levels of accuracy were obtained from combing the results from vaginal and rectal swabs, this showing an 84% sensitivity and 87% specificity. However, this was considerably lower than the pooled estimates from a meta-analysis of all the previous studies[42] which reported a pooled sensitivity and specificity of 97% for PCR. This discrepancy may have arisen since, with more robust methodology, GBS1 avoided overestimation of accuracy associated with review bias and other features prevalent in previous studies.[43] Updating the meta-analysis to include results from GBS1 reduced the pooled estimates for PCR to a new pooled sensitivity of 90% (95% CI 88-93%), and pooled specificity of 92% (95% CI 91-94%). The accuracy of the PCR, when considering samples from both sites, compares favourably with that of screening by culture of swabs taken at 35-37 weeks gestation.

In GBS1 we found that it was possible to train midwifery staff to undertake complex testing required by the Cepheid IDI-GBS and SmartCycler system, but it was not feasible to establish testing on demand. As the study progressed, we found that fewer tests were done in real-time but were instead samples were stored before being processed in batches. This was possible since, in GBS1, prophylaxis was not directed by the results of the rapid test. In GBS2, even when processing started immediately, there were considerable difficulties in ensuring the availability of results within the timescale that would have been required clinically. These mainly related to problems in ensuring the ongoing availability of sufficient staff who were competent to undertake testing, the fact that it was impossible when undertaking tests that require significant hands-on test time for staff to begin processing another sample when one was already in progress, as well as the conflicting demands on the midwifery staff.

Development of molecular methods that allow rapid bedside detection of microorganisms offers the potential to target antibiotic use more specifically than was previously possible. GBS1 showed that implementation of complex point of care (POC) tests is technically feasible. However the practical value of any POC test depends on accurate results being reliably available within a clinically relevant timeframe. To this end, careful consideration is required of a number of factors including the expected frequency of testing, achievable result turnaround times, the amount of hands-on test time, strategies to deal with test failure, and assurance of the ongoing availability of sufficient staff able to undertake testing when required.

The majority of the commercially available test systems require multiple preparation and incubation steps comparable to the previous generation Cepheid Smart-Cycler system. In light of the limitations found with this system in GBS1, the technology that we propose to investigate is the Cepheid GeneXpert system. The GBS Xpert test for this platform allows accurate detection of GBS within 35 minutes of placing an appropriate sample in the machine, with a hands-on preparation time of less than 2 minutes.

Existing research related to Cepheid GeneXpert GBS system

The Cepheid GeneXpert GBS system has been available since 2008 and several groups have assessed its accuracy in studies, although with different swabbing strategies and reference standard comparators. A systematic search of test evaluation studies and randomised comparisons of screening strategies using the Cepheid GeneXpert GBS system has been undertaken. Searches were made of Medline, Embase, Cochrane Clinical Trial Register, Cochrane Database of Systematic Reviews and the International Clinical Trial Registry Portal (ICTRP), from 2008 to the present (the GeneXpert GBS system received a CE mark in 2009) using search terms (group B streptococcus or streptococcus agalactiae) and (GeneXpert or pcr) and (identif\$ or screen\$ or diagnos\$ or test\$).

The search identified 15 test evaluation studies, from which data for meta-analysis could be extracted from 11 studies. There is one ongoing single centre study registered on ICTRP, at a UK private hospital, of which we were already aware. There were no randomised comparisons of strategies.

The majority of studies excluded pre-term and precipitate deliveries. Double or triple swabs were invariably used to minimise sampling differences and 8 took rectovaginal swabs. From a meta-analysis of 9 studies that used an enriched culture method for the reference standard, we obtained estimates of the average accuracy of the test of sensitivity 96.4% (90.8-98.6) and specificity 98.9% (97.5-99.5). Overall, the quality of the studies was adequate, but the potential for bias remained, mainly from a lack of blinding, use of only vaginal swabs or an inappropriate reference standard that could underestimate colonisation rates, remains.

[figure not shown]

Figure 9. Receiver-operative curve for 8 GeneXpert accuracy studies

Better targeting of IAP

Existing UK guidelines (RCOG, NICE) and the National Screening Committee advocate a risk based approach to the prevention of neonatal early-onset GBS sepsis. This approach results in 20-30% of women receiving antibiotics. GBS1 showed that only two thirds of women with risk factors are colonised with GBS and compliance with national guidelines varies in practice.[59] Thus antibiotic exposure could be considerably reduced if targeted only at those women in labour who are shown to be colonised with GBS.

Version 1.0 22nd December 2015

GBS2

Page 58 of 81

A study in France assessed whether rapid intrapartum screening for GBS using the Cepheid GeneXpert system reduced the proportion of women unnecessarily administered IAP in comparison with a hypothetical situation where the French national screening programme standard prevailed. [60] The investigators assessed the diagnostic performance of the rapid test to detect the presence of GBS on vaginal swabs taken during the intrapartum period. These results were compared with microbiological screening at 34-38 weeks' gestation and a reference standard of microbiological culture, albeit using a non-standard method. Preterm deliveries (less than 35 weeks' gestational age) were excluded and the rapid tests were performed by laboratory technicians and junior doctors.

Administration of IAP was directed during the study by the result of the rapid test, and the adequacy of this strategy compared against that which would have been hypothetically followed by use of the 34-38 week culture result. This matched pair design allows each woman to act as her own control, but overestimates the adequacy of the antenatal screening strategy.

Only 4.5% of the women in the study arm using the rapid test were found to have received IAP unnecessarily. This rose to 13.6% of the women where the results of the 34-38 week culture were used to direct antibiotic administration. This study demonstrates that the use of a rapid test can substantially reduce the administration of unnecessary IAP in comparison with a tissue culture technique.

A more rigorous, randomised evaluation of the rapid test against the current UK policy of risk-factor directed IAP is required. An assessment of diagnostic performance of the same rapid test performed by midwives in a clinical rather than laboratory setting, would verify whether the results of the meta-analysis described above remain applicable. In their study, Poncelet-Jasser *et al* [60] potentially underestimated the prevalence of GBS (and hence the predicative values of the test) by taking only vaginal swabs, and excluding pre-term deliveries.

Furthermore, assessment of neonatal outcomes, to include impact on EOGBS disease and neonatal death, are needed to inform an economic evaluation that goes beyond the outcome of cost per case of unnecessary IAP avoided.

Finally, providing paediatricians with the maternal GBS colonisation status during labour has the potential to reduce the number of babies who are treated with unnecessary antibiotics in the postpartum period, as well as shortening the duration of antibiotic treatment in those babies who commenced prophylaxis antibiotic administration after receiving insufficient exposure during their mother's labour.

The need to reduce the use of antibiotics and spread of resistance

Currently, at least 10% of all babies born in the UK are treated with intravenous antibiotics, despite the fact that the incidence of early-onset neonatal sepsis is very low at 0.48 per 1000 births.[32] As a result, tens of thousands of babies are kept in hospital at considerable cost to the NHS and receive intravenous antibiotics that may be unnecessary. As well as encouraging the emergence of an increasing number of antibiotic resistant superbugs, recent research has highlighted a number of not insignificant risks arising from exposure of the foetus and new-born infant to antibiotics. These may include a heightened risk of developing necrotising enterocolitis, [60, 61], inflammatory bowel disease,[62] fungal infection,[63] and cerebral palsy.[64]

Antibiotic resistance is regarded by many as an imminent threat to human health. The international importance of this issue is reflected by the call for action from the World Health Organisation[61] and recent reports by the Centre for Disease Control in the US[62] and Public Health England in the UK[63].

Antibiotic (treatment) resistant bacteria have been increasingly shown to cause early and late onset neonatal sepsis[65, 66], and neonatal intensive care unit (NICU) sepsis outbreaks.[67, 68] Strategies for control have focused on reducing the selection pressure (antibiotic stewardship) and control of the spread of the resistant strains. Carriers of antibiotic resistant microbes can be identified by screening and actions taken to prevent spread to others include the implementation of contact precautions and decontamination of the colonised individual. By contrast with methicillin-resistant $Staphylococcus\ aureus$ (MRSA), there is currently no reliable method of decontamination of individuals colonised with antibiotic resistant Enterobacteriaceae including those with extended spectrum β -lactamases (ESBLs). ESBLs have recently emerged in community acquired $Escherichia\ coli$ and $Klebsiella\ pneumonia$, and their identification as causal agents of infections in neonatal units and the lack of effective therapeutic options is a worrying development.

Transmission of bacteria from mothers to their infants has been well documented. Studies have predominantly focused on the causative agents of early neonatal sepsis – *Streptococcus agalactiae*, GBS, and *E. coli*.[69, 70] Risk factors for neonatal colonisation with ESBLs have been described but the relative contribution of perinatal vertical transmission as opposed to horizontal acquisition is uncertain.[71] The reported prevalence of *E. coli* vaginal colonization in pregnant women ranges from 7% to 20%.[72, 73] One study from Argentina reported peri-anal colonization with ESBL-producing *E.coli* in 5.4% of pregnant women.[74]

As part of an Olympics surveillance project (in collaboration with Public Health England) ESBL-producing *Enterobacteriaceae* were isolated from 20% of women of child bearing age (15-45 years) in North-East London who submitted a faecal sample for laboratory examinations.[75] At the same time colonisation with ESBL-producing

Enterobacteriaceae has been demonstrated in 7% of NICU infants of less than 31 weeks gestational age recruited into a multi-centre, double blind, placebo-controlled randomised probiotic feeding study in South-East England (PIPS study, personal correspondence). The extent to which NICU infant colonisation reflects perinatal vertical transmission is currently unclear.

11. SAFETY REPORTING

GBS2 is a study comparing two screening policies and is not a clinical trial assessing the efficacy of an investigational medicinal product. This is reflected by the degree of study specific adverse event reporting in GBS2.

Direct risks of screening policies

The risk based screening approach involves the noting of historical risk factors and the monitoring of women for emerging risk factors such as chorioamnionitis. This presents no risk to the women other than a failure to identify and act upon these risk factors.

The rapid test screening requires a vaginal / rectal swab to be collected during labour, which is benign and presents no foreseeable risk of harm. As with almost any diagnostic test, there is a risk that testers may suffer an inoculation injury (most likely mucous membrane exposure) with clinical material. Every effort will be made to minimise this risk through training and provision of appropriate personal protective equipment and a safe working environment. In the event of such an incident, the local Trust policy for the management of inoculation injuries will be followed.

Risks arising from antibiotic regimens

There may be adverse events as a result of administering benzylpencillin, either to the mother or baby. The most significant of these is an anaphylactic reaction which requires immediate treatment with adrenaline. Lesser degrees of hypersensitivity are common and a rash (all forms), fever or serum sickness observed in 1-10% of recipients. Depending on their underlying cause, these adverse reactions may be treated with antihistamines.

There may be significant consequences of the failure to offer IAP to a woman with GBS risk factors, or who the rapid test identifies as being colonised with GBS, in terms of the potential vertical transmission of GBS to their baby and its increased risk of developing EOGBS disease. Conversely, there is a risk of overtreatment if women without risk factors, or with a negative rapid test, have IAP administered. These instances are considered outcomes of interest within the study, and not adverse events.

Despite either screening approach, there may be babies who develop a superficial or systemic infection, including EOGBS disease. Again, these are defined as outcomes, rather than adverse events, within the study.

Reporting adverse events of testing or antibiotic administration

The following need to be reported as adverse events:

- Inoculation injury to the clinical staff either whilst taking the swab or using the GeneXpert system
- Anaphylaxis in the mother following IAP or her child following antibiotic treatment

Notification and reporting of Serious Adverse Events

Should either event occur then local hospital and Yellow Card reports should be submitted as per trust policy, and the event should be reported to the trials office using an SAE form within 24 hours of learning of the event. The sponsor will coordinate submission of the SAE to the main REC within 15 days in line with the required timeframe.

GBS2 is not assessing the efficacy of antibiotics *per se*, so the clinical trial concept of a suspected, unexpected serious adverse reaction is not applicable here. Serious adverse intrapartum and neonatal outcomes, including but not limited to birth asphyxia, post-partum haemorrhage, neonatal consequences of prematurity and neonatal death are not considered adverse events.

Annual Safety Reporting

The CI will send the Annual Progress Report to the main REC using the NRES template (the anniversary date is the date on the MREC "favourable opinion" letter from the MREC) and to the sponsor.

Overview of the Safety Reporting responsibilities

The CI/PI has the overall oversight responsibility for GBS2. The CI/PI has a duty to ensure that safety monitoring and reporting is conducted in accordance with the sponsor's requirements.

12. MONITORING & AUDITING

The CI will ensure that GBS2 is conducted in compliance with the principles of the Declaration of Helsinki (1996), and in accordance with all applicable regulatory requirements including but not limited to the Research Governance Framework, GCP, Trust and Research Office policies, procedures, and any subsequent amendments.

Non-Compliance is defined as a noted systematic lack of both the CI and the study staff adhering to the principles of the Declaration of Helsinki (1996), applicable regulatory requirements including, but not limited to, the Research Governance

22nd December 2015

Framework, GCP, Trust and Research Office policies and procedures and any subsequent amendments, which leads to prolonged collection of deviations, breaches or suspected fraud.

These non-compliances may be captured from a variety of different sources including monitoring visits, collected data, communications and updates. The sponsor will maintain a log of any non-compliance to ascertain if there are any trends developing or escalating. The sponsor will assess the non-compliance and action a timeframe in which they need to be dealt with. Each action will be given a different timeframe dependent on the severity. If the actions are not dealt with accordingly, the sponsor will agree an appropriate action. This may include an on-site audit.

Due to the nature of the source data, the use of transferred electronic data, and the low risk of harm to the women delivering in the maternity units, a central monitoring approach will be adopted.

Notwithstanding this principle, investigators and their host Trusts will be required to permit any study-related monitoring and audits to take place by the sponsor or their nominated monitor, providing direct access to source data and site file documents as requested. Trusts may also be subject to inspection by the Research and Development Manager of their own Governance Team and should do everything requested by the Chief Investigator in order to prepare and contribute to any inspection or audit.

Data transfer quality control

A bespoke computer database will be constructed for the GBS2 trial data and will include range and logic checks to prevent erroneous data entry. Independent checking of data entry will be periodically undertaken on small sub-samples. All data merging programs and macros will be tested prior to acceptance of the system.

To ensure the smooth running of the trial and to minimise the overall procedural workload, it is proposed that each participating centre should designate different individuals who would be chiefly responsible for local co-ordination of either the clinical, policy and administrative aspects of the GBS2 study.

All investigators are responsible for ensuring that any research they undertake follows the agreed protocol. This includes ensuring that women with GBS risk factors are screened according to the assigned strategy for that unit, that 'at risk' women and babies are provided with IAP according to NICE / RCOG guidelines, and to protect the integrity and confidentiality of clinical and other records and data generated by the research, and for reporting any failures in these respects, adverse events or suspected misconduct through the appropriate systems.

13. TRIAL COMMITTEES

Independent Trial Steering Committee (TSC)

The TSC provides independent supervision for the trial, providing advice to the funder, Sponsor, Chief and Co-Investigators on all aspects of the trial as well as affording protection for patients by ensuring the trial is conducted according to the MRC Guidelines for Good Clinical Practice in Clinical Trials.

If the Chief and Co-Investigators are unable to resolve any concern satisfactorily, Principal Investigators, and all others associated with the study, may write via the Trial Office to the chair of the TSC drawing attention to any concerns they may have about the implementation of the study or about any other matters thought relevant.

DMEC: determining when clear answers have emerged

If the use of a rapid test screening strategy for GBS really is substantially better or worse than risk factor alone based screening with respect to the rate of IAP administration then this may become apparent before the target number of participants has been reached or the total number of maternity units have been deployed. Alternatively, new evidence might emerge from other sources or NHS policy may change. To protect against this, during the rapid test implementation period of the study, interim analyses of the primary outcome will be supplied, in strict confidence, to an independent Data Monitoring and Ethics Committee (DMEC) along with updates on results of other related studies, and any other analyses that the DMEC may request. The DMEC will advise the chair of the Trial Steering Committee if, in their view, the randomised comparisons has provided both (a) "proof beyond reasonable doubt" that for all, or for some, types of labouring women, a particular strategy is definitely indicated or definitely contraindicated, in terms of a net difference in the primary outcome, or that the rapid test was demonstrating unanticipated poor accuracy and (b) evidence that might reasonably be expected to influence the National Screening Committee. The TSC can then decide whether to close or modify any part of the trial. Unless this happens, however, the TMG, TSC, the investigators and all of the central study staff (except the statisticians who supply the confidential analyses) will remain unaware of the interim results.

Members of the various committees are shown in the appendix.

¹ Appropriate criteria of proof beyond reasonable doubt cannot be specified precisely, but a difference of at least three standard deviations in an interim analysis of the primary outcome may be needed to justify halting, or modifying, the study prematurely. If this criterion were to be adopted, it would have the practical advantage that the exact number of interim analyses would be of little importance, so no fixed schedule is proposed.

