A sample size of 676 would provide 90% chance of us accruing enough GBS colonised women to have 90% power to show the sensitivity of the GBS test to be statistically significantly (with p<0.05) greater than 90% should the meta-analytical estimate of its performance (96.4%) be correct whilst allowing for 10% loss from failed tests, based on the GBS prevalence observed in GBS1, which was 29.8% (89/299, 95% CI: 24.6%-35.2%). Of the 606 participants with data we would expect 167 to be GBS carriers and 439 to be negative for GBS colonisation. If the prevalence of GBS colonisation is actually at the lower 95% confidence interval from GBS1, namely 24.6%, then 673 total women will give 90% chance of observing 136 cases of GBS colonisation, including 10% lost tests.

The 95% Cis we would observe on sensitivities and specificities of 85%, 90%, 95% and 98% with a sample size of 676 (606 with data) are shown in **Table 1** and have adequate precision (sensitivity within 10%, specificity within 6%) for modelling.

Point estimate	CI for sensitivity (n = 167)	CI for specificity ($n = 439$)
85	78.7 – 90.1	81.3 – 88.2
90	84.2 – 94.0	86.8 – 92.7
95	90.9 – 97.9	92.5 – 96.8
98	94.8 – 99.6	96.2 – 99.1

Table 1: Confidence Intervals for sensitivity and specificity at various point estimates Cluster

randomised trial

The focus of this sample size calculation is on the effectiveness of the rapid GBS test within a cluster randomised trial (CRT) in which the number of clusters, in this case maternity units, is limited by the by the willingness of NHS Trusts to participate, but the number of potential participants is only limited by the duration of study period.

The CRT requires a minimum of 8 maternity units per screening strategy i.e. a total 16 units. Based on assumptions cited below, we estimate that the sample size per cluster will be approximately 83. This equates to a total sample size of approximately 664 participants per arm, and so therefore allows sufficient numbers of women to be recruited for the test accuracy study too.

As there are two arms (Standard Practice / Rapid Test), each of at least 664 participants this gives a projected sample size of 1,328 women. This has been rounded up to a target sample size of 1,340 women.

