Primary analysis will be unadjusted, but secondary analyses will adjust for prespecified and clinically important baseline covariates. These will include gestational age, and presence of individual risk factors, and maternity unit level covariates such as size. We will allow for clustering at the maternity unit level. The primary analysis will be a complete case analysis. However, missing data will be reported and associations between outcomes explored. Depending on the nature of these associations and the extent of the missing data, sensitivity will be explored by means of multiple-imputation.

The primary outcome will be considered significant at the 5% level (and so the 95% Cis reported); whereas other secondary outcomes will be interpreted cautiously as the CRT is not necessarily powered to detect a difference in these. Reports of interim analysis will be supplied in confidence to the DMEC during the recruitment period. Final analysis will be performed once all babies born to mothers in the study have reached six months of age.

Relatedness sub-study

The proportions of mothers and infants carrying antibiotic resistant bacteria will be documented and the degree to which the strains are indistinguishable when characterised using techniques which include; matrix-assisted laser desorption ionization—time of flight mass spectrometry, antibiotic susceptibility profile, and genetic analyses (including analysis of resistance mechanisms) will be documented. These data will allow an estimate of the extent to which mothers and infants at around six weeks of post-natal life carry indistinguishable strains of resistant bacteria. This data will be used to inform the design of more detailed studies aimed at better understanding transmission pathways with the objective of defining potential interventions.

Accrual and study initiation roll-out

We will not attempt to start recruitment in all sites simultaneously but instead plan on opening equal numbers of control and experimental sites in staggered waves. The burden of supporting sites will be spread over 12 months and lessons learnt in the first wave will be carried forward to the management later units.

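### With 16 maternity units opened in up to four waves, a three-SD interim criterion does not make the number and timing of looks unimportant

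*Protocol*

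**What the plan says.** Section 13, under the DMEC heading, states that "interim analyses of the primary outcome will be supplied, in strict confidence, to an independent Data Monitoring and Ethics Committee". It foresees that a clear answer may emerge early: "this may become apparent before the target number of participants has been reached or the total number of maternity units have been deployed". The footnote says that proof beyond reasonable doubt has no exact definition, and offers one possible yardstick: "a difference of at least three standard deviations in an interim analysis of the primary outcome may be needed to justify halting". The same yardstick is offered for altering the trial early. On the condition that the DMEC takes it up, the footnote reasons as follows: "it would have the practical advantage that the exact number of interim analyses would be of little importance, so no fixed schedule is proposed".

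The design facts that bear on this are elsewhere in the protocol:

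- Statistical Considerations, Cluster randomised trial: "The CRT requires a minimum of 8 maternity units per screening strategy i.e. a total 16 units", with about 83 women per unit.
- Randomisation of maternity units: clusters are randomised in up to four waves.
- Accrual and study initiation roll-out: the team will "plan on opening equal numbers of control and experimental sites in staggered waves". Site support is spread over 12 months, while each site needs a study period of only 4-5 weeks.
- Analysis methods: the primary outcome is analysed with population-averaged models fitted by GEE. The protocol mentions no small-sample correction.

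**The concern.** A three-SD interim boundary is a sound device when the test statistic is close to normal. Its tail is then so small that repeated looks add little. The footnote relies on that property to justify having no schedule.

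In a cluster trial the precision of the comparison is estimated from the variation between units. With few units that estimate is unstable, the statistic has heavy tails, and three estimated SDs can be reached by chance far more often than the normal figure suggests. The risk falls steeply as units accrue, so when the committee looks, and how often, matters a great deal.

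At stake is a signal from a handful of units being read as near-proof. The accuracy study draws its women from the rapid-test arm, so a decision to close that arm early could shorten it too. That would not follow automatically, because the TSC may close or modify only part of the trial.

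**Working it through.** **Inputs.** At least 16 units, 8 per arm; up to four waves, balanced by arm; about 83 women per unit; control IAP rate 75% (60% also tabulated); ICC 0.01 to 0.2; GEE analysis; criterion of three SD with no error rate attached. All are from the protocol sections named above.

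**The plan's own figures.** The protocol gives no error rate for the interim criterion, so there is none to reproduce. Its sizing can be checked. At ICC 0.01 the design effect is 1 + 82 × 0.01 = 1.82, so 664 women per arm are worth 664 / 1.82 = 364.8. For 75% against 63.2%, the SE is √[(0.1875 + 0.2326) / 364.8] = 0.0339. With t quantiles on 16 − 2 = 14 df, the detectable difference is (2.145 + 1.345) × 0.0339 = 0.118, or 75% to 63.2% (Table 2 says 63%). Seven of the eight cells in Table 2 agree to rounding on this t basis; normal quantiles fit less well.

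**Clusters at each look.** With four equal waves, 16 / 4 = 4 units per wave, two per arm. Looks after waves 1, 2 and 3 hold 4, 8 and 12 clusters.

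**Normal reference.** The two-sided tail beyond 3 is 0.27% per look. Cumulatively it is about 0.8% over four looks, 1.4% over ten and 3.5% over a hundred. On this reference the footnote's argument roughly works.

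**Cluster-level t reference**, with clusters minus 2 df. For 2 df the two-sided tail is 1 − 3/√(2 + 9) = 1 − 0.9045 = 9.5%. For 6 df, with sin θ = 3/√15 = 0.7746 and cos²θ = 0.4, it is 1 − 0.7746 × (1 + 0.4/2 + 3 × 0.16/8) = 1 − 0.7746 × 1.26 = 2.4%.

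**GEE robust z**, by null simulation: 200,000 replicates, beta-binomial outcomes, 83 women per unit, IAP rate 50-75%, ICC 0.01-0.2. The range in the table runs from a variance inflated by K/(K − 1), for K clusters, to no correction.

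| Clusters | df | t tail beyond 3 | Multiple of 0.27% | GEE robust z beyond 3 | t value giving 0.27% |
|---|---|---|---|---|---|
| 4 | 2 | 9.5% | 35 | 13-17% | 19.2 |
| 8 | 6 | 2.4% | 9 | 3-4.5% | 4.90 |
| 12 | 10 | 1.3% | 5 | 1.5-2.3% | 3.96 |

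**Cumulative crossing with no true difference:**

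- Looks at 4, 8 and 12 clusters: about 12% with the t statistic, 15-16% with the robust z and K/(K − 1), and 18-20% with the uncorrected robust z.
- Looks at 8 and 12 only: about 3%, 4% and 5% respectively.

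The results barely change with the ICC. If the between-cluster variance were known, the rate would be only 0.06-0.3% per look. The excess therefore comes from estimating that variance from few clusters.

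**The case against.** The strongest reply is that the footnote contains no rule. Three SD is something that may be needed, if adopted. The DMEC must also judge whether the evidence would influence the National Screening Committee; it then only advises, and the TSC decides. This stands: the figures above are chances of crossing a boundary and cap the chance of a false stop. They should not be read as a 12-20% false-stopping rate. But the decision to set no schedule is made outright in the protocol, and the argument given for it is wrong for this design.

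Second, four waves and a look at 2 against 2 units are assumptions. The protocol says up to four waves and schedules no look. This also stands, and most of the cumulative figure comes from that first look. With two waves, however, the first look would hold 8 clusters and the t tail is still 2.4%, nine times the normal value.

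Third, the interim reference distribution may be set in an SAP or DMEC charter. Table 2 suggests that the authors did allow for few clusters in sizing the trial. So the missing correction is not in itself the fault. The fault is the stated claim about the number of looks, which a later document would have to contradict.

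A reader might also infer a total type I error near 20%. The documents do not support attributing that to the interim plan: a final z-test on 16 clusters without correction already rejects about 8% of the time with no looks at all. Nor is neonatal safety shut out of the interim package, since the DMEC may request any other analyses.

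**Conclusion.** The point holds as an error in a stated justification. For 16 maternity units in up to four balanced waves, the number and timing of looks are not of little importance under a three-SD criterion. Chance crossing per look is about 9.5%, 2.4% and 1.3% at 4, 8 and 12 clusters on a t statistic, and somewhat higher with a GEE robust z, against 0.27% for a normal one. Cumulatively it is about 12-20% over three looks, or about 3-5% if none is taken at 4 clusters.

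This rests on four equal waves, looks at the end of a wave, equal cluster sizes of 83, and a three-SD threshold applied without small-sample adjustment. The 0.27% benchmark is the normal tail implied by three SD; the protocol does not state it as an intended error rate.

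**What to change.** In the Section 13 footnote:

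1. Delete the statement that the number of interim analyses would be of little importance.
2. Express the criterion as a two-sided p-value of about 0.0027, or stricter, on a small-sample reference: t with clusters minus 2 df, or a GEE with a small-sample correction.
3. State a minimum number of completed clusters per arm before the criterion is applied, for example 4 per arm.

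The exact threshold, the minimum and any fixed timing of looks are for the sponsor and the DMEC to choose. The change affects only the footnote and the DMEC charter. Its price is that early stopping becomes less likely: at 8 clusters a t value of 4.90 would be needed in place of 3. That costs little, because each unit recruits for only 4-5 weeks.
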